### **9.4 Adverse Events**

All adverse event summaries will be restricted to Treatment Emergent Adverse Events (TEAE), which are defined as those AEs that occurred after first CPX-POM dosing and those existing AEs that worsened during the study. This will not include AEs that are due to the operative TURBT procedure. If it cannot be determined whether the AE is treatment emergent due to incomplete or missing data, then it will be considered treatment emergent. Verbatim terms will be mapped to preferred terms and system organ classes using the Medical Dictionary for Regulatory Activities (MedDRA) (version 23.1).

Summaries that are displayed by system organ class and preferred terms will be ordered by descending order of incidence of system organ class and preferred term within each system organ class. The following summaries will be provided:

- Overall summary of AEs
- TEAEs by system organ class and preferred term
- TEAEs by system organ class, preferred term, and highest intensity
- Related TEAEs by system organ class and preferred term
- Serious TEAEs by system organ class and preferred term
- Serious Related TEAEs by system organ class and preferred term
- TEAEs leading to study discontinuation by system organ class and preferred term
- TEAEs resulting in death

Related events will be any event having the causality field marked as “Related” or missing on the Adverse Event eCRF page. Intensity (Grade) of AEs will be based on the NCI Common Terminology Criteria for Adverse Events (CTCAE) (5.0).

All AEs will be provided in a listing.

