Study Design:	
This will be an open-label study to determine the safety, dose tolerance, pharmacokinetics, and pharmacodynamics of CPX-POM in patients with newly diagnosed or recurrent, untreated or intravesical treatment completed >6 months before the current diagnosis, resectable tumors. Approximately 12 patients will be enrolled and treated with 900 mg/m² CPX-POM administered IV over 20 minutes once per day for 5 days followed by TURBT on Day 5 after the fifth dose. TURBT will be performed 2 to 6 hours following drug administration on Day 5.
 
Pretreatment bladder tumor tissues will be obtained at the time of in-office cystoscopy by cold cup biopsy within 4 weeks of TURBT. Posttreatment bladder tumor tissues will be obtained at TURBT. Bladder tumor tissues will undergo pathological evaluation at each site.
 
Prior to administration of the first CPX-POM dose on Day 1, pre-dose blood (plasma) and urine (clean catch) samples will be collected. At the time of TURBT on Day 5, one 3-mL blood (plasma) sample and a urine specimen will be collected for measurement of CPX-POM concentrations.
 
Patients will be followed for at least 30 days after the last dose of CPX-POM for safety.

Number of Patients Planned:	Approximately 12 patients will be enrolled.
Target Population:	The target population for this study is patients with newly diagnosed bladder tumors, inclusive of recurrent disease, who are treatment-naïve or had treatment completed >6 months before screening, and will be scheduled to undergo TURBT
Duration of Study:	Patients will be in this study for approximately 9 weeks: up to a 28-day screening period, a 5-day treatment period, and a 30-day follow-up period.
Diagnosis and Main Eligibility Criteria:	Patients eligible for enrollment will be adults who are likely to have a new bladder tumor based on clinical presentation or who are at high risk for tumor recurrence based on previous history, which is subsequently confirmed cystoscopically and will be scheduled to undergo TURBT. Patients must be treatment-naïve or had treatment completed >6 months before screening, and have an estimated glomerular filtration rate (eGFR) >30 mL/min/1.73 m ² .
Test Product, Dose, and Mode of Administration:	Patients will begin treatment with CPX-POM on a Monday, 4 days before the date of scheduled TURBT on a Friday. Patients will receive CPX-POM 900 mg/m ² by 20-minute IV infusion once daily for 5 days followed by TURBT after the last dose on Day 5.

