3. Pre-treatment bladder tumor tissue sample will be obtained during in-office cystoscopy by cold cup biopsy within 4 weeks of TURBT. Post-treatment bladder tissue sample will be obtained at surgical resection (TURBT) on Day 5.
4. Hematology will include measurement of hemoglobin, hematocrit, platelets, RBC, reticulocytes, and WBC with differential.
5. Clinical chemistry will include measurement of potassium, sodium, chloride, glucose, BUN, creatinine, creatinine clearance, ALT, AST, GGT, alkaline phosphatase; indirect bilirubin, direct bilirubin, total bilirubin, total protein, albumin, calcium, bicarbonate, magnesium, phosphate, lipase, and amylase.
6. Urinalysis will include color, turbidity, pH, specific gravity, glucose, ketones, nitrites, bilirubin, urobilirubin, protein, RBCs, WBCs, epithelial cells, casts, crystals, and bacteria, and eGFR at Screening only.
7. A full physical examination will be conducted at Screening and at Visit 7/Follow-up. At each other study visit, patients will be assessed for continued dosing and any possible physical symptoms/toxicities and a physical examination may be performed, if indicated. Body weight should be measured at each study visit. Height should be measured at Screening.
8. Vital signs will be measured before any blood draws scheduled for the same time point. Vital signs will include blood pressure, respiratory rate, pulse, oxygen saturation, and temperature.
9. At Screening, 12-lead ECGs will be performed in triplicate, with each measurement separated by 2 minutes. The average of the 3 screening ECGs will be used to calculate QTc interval to determine study eligibility. Thereafter, single 12-lead ECGs will be performed for all patients prior to drug administration on Days 1 and 5 and at the Final Study visit.
10. All AEs and SAEs will be collected from the signing of the informed consent form through the time of TURBT. Starting at TURBT, only AEs related to CPX-POM treatment should be recorded; AEs related to the TURBT will not need to be recorded.
11. All concomitant medications will be recorded from the time of Screening up to the time of TURBT. Starting at TURBT, only medications associated with an AE related to CPX-POM treatment need to be recorded; routine medications and medications associated with the TURBT procedure do not need to be recorded.

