8. STUDY ASSESSMENTS

8.1. Safety Assessments

8.1.1. Adverse Events and Serious Adverse Events

8.1.1.1. Definitions

Adverse Event

An AE is any untoward medical occurrence in a clinical investigation subject administered a medicinal product and which does not necessarily have a causal relationship with this treatment. An AE can therefore be any unfavorable and unintended sign, symptom, or disease temporally associated with the use of a medicinal product, whether or not considered related to the medicinal product.

AEs also include the following:

- Pre- or post-treatment complications that occur as a result of protocol mandated procedure (e.g., such as venipuncture, biopsy) during or after Screening (before the administration of study investigational medicinal product).
- Any pre-existing condition that increases in severity, or changes in nature during or as a consequence of the study investigational medicinal product phase of a human clinical trial, will also be considered an AE.
- Complications and termination of pregnancy (see Section [8.1.2](#) for additional information)
- All AEs that occur from the study screening visit onwards and throughout the duration of the study, including the follow-up off study medication period should be recorded as an AE.

An AE does not include the following:

- Medical or surgical procedures (e.g., surgery, endoscopy, tooth extraction, transfusion) performed; the condition that leads to the procedure is an AE.
- Pre-existing diseases or conditions or laboratory abnormalities present or detected before the screening visit that do not worsen.
- If progression of underlying malignancy is clearly consistent with the suspected progression of the underlying cancer as defined by the Response Evaluation Criteria in Solid Tumors (RECIST) 1.1, or with clinical symptoms (clinical progression), it should not be reported as an AE/SAE. Similarly, hospitalization due exclusively to the progression of underlying malignancy should NOT be reported as an SAE.

- Situations where an untoward medical occurrence has not occurred (e.g., hospitalization for elective surgery, social and/or convenience admissions).
- Any medical condition or clinically significant laboratory abnormality with an onset date before the consent form is signed and not related to a protocol-associated procedure is not an AE. It is considered to be pre-existing and should be documented on the medical history case report form (CRF).
- Uncomplicated pregnancy.

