- Other situations. Medical or scientific judgment should be exercised in deciding whether SAE reporting is appropriate in other situations such as important medical events that may not be immediately life-threatening or result in death or hospitalization but may jeopardize the patient or may require medical or surgical intervention to prevent one of the other outcomes listed in the above definition. These events should usually be considered serious. Examples of important medical events include invasive or malignant cancers, intensive treatment in an emergency room or at home for allergic bronchospasm, blood dyscrasias or convulsions that do not result in hospitalization, or development of drug dependency or drug abuse.

8.1.1.2. Time Period and Frequency for Collecting Adverse Event and Serious Adverse Event Information

All AEs and SAEs will be collected from the signing of the informed consent form (ICF) through the Follow-up visit (28 +/- 5 days after the last dose of study drug).

Medical occurrences that begin before the start of study intervention but after obtaining informed consent will be recorded on the Medical History/Current Medical Conditions section of the CRF not the AE section.

Investigators are not obligated to actively seek AE or SAE after conclusion of the study participation. However, if the investigator learns of any SAE, including a death, at any time after a patient has been discharged from the study, and he/she considers the event to be reasonably related to the study intervention or study participation, the investigator must promptly notify the Sponsor.

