9.5.1. Adverse Events

Clinical and laboratory AEs will be coded using the Medical Dictionary for Regulatory Activities (MedDRA). SOC, High-Level Group Term (HLGT), High-Level Term (HLT), Preferred Term, and Lower-Level Term (LLT) will be attached to the clinical database.

AEs will be summarized on the basis of the date of onset for the event. A treatment-emergent AE will be defined as any AE that begins on or after the date of first dose of CPX-POM.

Summaries (number and percentage of patients) of treatment-emergent AEs (by SOC, and Preferred Term) will be provided by dose group/cohort and overall.

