### **Start Dates**

- If the day portion of the start date is missing, then the start date will be estimated to be equal to the date of first dose of study drug, provided the start month and year are the same as the first dose of study drug and the stop date is either after the first dose of study drug or completely missing. Otherwise, the missing day portion will be estimated as '01'.
- If both the day and month portions of the start date are missing, then the start date will be estimated to be equal to the date of first dose of study drug, provided the start year is the same as the first dose of study drug and the stop date is either after the first dose of study drug or completely missing. Otherwise, the event will be assumed to start on the first day of the given year (e.g., ??-??-2021 is estimated as 01-JAN-2021).
- If the start date is completely missing and the stop date is either after the dose of study drug or completely missing, the start date will be estimated to be the day of study drug dosing. Otherwise, the start date will be estimated to be the first day of the same year as the stop date. All other non-AE and non-concomitant medication day calculations where only partial dates are available will be handled as follows: the first day of the month will be used in the calculations if the day part of a start date is missing while January 1 will be employed if both the month and day parts of a start date are missing.

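### SAP 9.4 does not tie worsening of adverse events to first dose, and SAP 5.1 can date a Day 1 event before treatment against the SAP's own default

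*SAP*

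**What the plan says.** **TEAE definition.** SAP 9.4 limits all AE summaries to TEAEs, "which are defined as those AEs that occurred after first CPX-POM dosing and those existing AEs that worsened during the study". It adds: "This will not include AEs that are due to the operative TURBT procedure". It also has a tie-break: an AE whose status cannot be settled because data are missing counts as treatment-emergent. Protocol 9.5.1 has a shorter rule: "A treatment-emergent AE will be defined as any AE that begins on or after the date of first dose of CPX-POM". That rule has no worsening clause and no exclusion for the resection (TURBT).

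**Incomplete dates.** SAP 5.1 opens with a conservative default: an incomplete onset is taken as on-treatment unless the partial date or other data, such as the stop date, point elsewhere. Its first two start-date bullets then impute the first-dose date only if the known parts of the start date match first dose and "the stop date is either after the first dose of study drug or completely missing". Otherwise they use day 01 of the month, or 1 January. The third bullet, for a wholly missing start, uses a similar stop-date condition and falls back to the first day of the stop year.

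**Events before dosing.** The protocol synopsis gives the study duration as "up to a 28-day screening period, a 5-day treatment period, and a 30-day follow-up period". Footnote 10 of the schedule (Protocol 1.3) says: "All AEs and SAEs will be collected from the signing of the informed consent form through the time of TURBT". Protocol 8.1.1.1 counts complications of a biopsy before study drug as AEs, and also "Any pre-existing condition that increases in severity, or changes in nature during or as a consequence of the study investigational medicinal product phase". Protocol 8.1.1.2 first collects AEs from consent, then says: "Medical occurrences that begin before the start of study intervention but after obtaining informed consent will be recorded on the Medical History/Current Medical Conditions". By that rule they stay off the AE page.

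**The concern.** Safety and dose tolerance are the primary objective, and the number of patients with treatment-related AEs is a secondary one. Every AE table for those objectives passes through the TEAE definition. Three gaps matter.

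- *Worsening.* The study begins at consent, so an AE that worsens in screening, before any drug, meets the literal wording.
- *The Day 1 boundary.* The SAP counts events after dosing, while the protocol counts events from the dosing date. The required source data in Protocol 10.2.5 name AE start and end dates but no clock time. Dates alone cannot say whether a Day 1 event came after the infusion.
- *Imputation.* The stop-date condition leaves out Day 1 itself, so a partly dated event that ended on Day 1 goes before treatment. A Day 1 stop date gives no evidence of a pre-dose onset.

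The first gap can raise counts, the third can lower them, and the second depends on how the programmer reads one word. Two analysts following the SAP could produce different tables.

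**Working it through.** The plan has no power or sample-size figure to reproduce: SAP 4 gives 12 patients without a calculation. The check is of the rules.

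**1. Length of the unanchored window** (synopsis). 28 + 5 + 30 = 63 days, which agrees with the stated 9 weeks or so. Up to 28/63 = 44% of a patient's planned time precedes first dose. This is a share of time, not of events.

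**2. The date rule in SAP 5.1.** Let D be the date of first dose and S the stop date. Read on dates, the condition is: S > D or S missing. If it holds, and the known parts of the start date match D, the imputed start is D. Otherwise it is:

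- day missing: the 1st of the start month;
- day and month missing: 1 January of the start year;
- start wholly missing: 1 January of the stop year.

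Coded this way, the rule reproduces the SAP's own example, in which an unknown day and month in 2021 become 1 January 2021.

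*One case.* Take D = Monday 7 June 2021 and an event that began and ended that day, with the start day missing. S > D is false, so the start becomes 1 June, 7 − 1 = 6 days before first dose. If S were 8 June, the start would be 7 June.

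*All cases.* The protocol starts dosing on a Monday. Each of the 52 Mondays of 2021 (year assumed from the SAP's example dates) was used as D, for an event that truly began on Day 1:

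| Start date | Stop date | Imputed before D | Imputed to D |
|---|---|---|---|
| Day missing | Day 1 | 49/52 | 3/52 |
| Day and month missing | Day 1 | 52/52 | 0/52 |
| Wholly missing | Day 1 | 52/52 | 0/52 |
| Any of the three | Day 2 or missing | 0/52 | 52/52 |

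The three exceptions are Mondays that fall on the first of a month. The fault needs both an incomplete start date and a stop on Day 1.

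**3. After the change to S ≥ D.** The Day 1 event is imputed to D in 52/52 cases for all three patterns. Under the protocol's rule (onset ≥ D) it is then a TEAE. Under a strict date-only reading of SAP 9.4 (onset > D) it still is not, so the definition must change as well.

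**4. Complete Day 1 onset date.** Onset = D. The protocol condition onset ≥ D is true; the strict SAP condition onset > D is false.

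**5. Size.** One patient reclassified: 1/12 = 0.083, or 8.3 percentage points. The documents do not allow the number of affected events to be computed.

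**The case against.** The case on the other side has force.

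- *The SAP may depart from the protocol.* Protocol 9 calls itself a summary and leaves the final plans to the SAP. This stands: the difference is not an error in itself, and Protocol 9.5.1 need not be amended. The Day 1 ambiguity inside the SAP remains.
- *Pre-dose worsening may never reach the AE page.* Protocol 8.1.1.2 sends events between consent and first dose to medical history. But footnote 10 and 8.1.1.1 point the other way, and the SAP's reference to existing AEs presupposes some. It does stand that worsening before any drug would hardly be judged related; SAP 9.4 would count it as related only if the causality field were blank.
- *The date fault is a corner case.* AEs are assessed at each dosing visit, and patients are observed for at least 1 hour after each infusion. A known stop day with an unknown start day should be rare. This stands.
- *Other SAP rules already protect the count.* The default and the tie-break both favour treatment-emergent. Imputing to the first-dose date would be pointless if an onset on that date did not count, which suggests that Day 1 is meant to be included. A stop later on Day 1 can also be read as after the dose. But no order of precedence is stated, and once a date has been imputed a programmer may see nothing left undetermined.

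A reader might infer that the protocol never counts a pre-existing condition that worsens on drug. The documents do not support that: Protocol 8.1.1.1 makes such worsening an AE in its own right, and if it is dated from the worsening it is a TEAE under 9.5.1. Only the dating is unstated.

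**Conclusion.** Two SAP rules are faulty as written: the worsening clause has no first-dose anchor, and the stop-date condition contradicts the SAP's default and tie-break for an incompletely dated event that ended on Day 1. The boundary wording on Day 1 is also unclear when only dates are held.

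It would be tempting to conclude that TEAE counts are wrong in both directions. The documents show only that they can be too high or too low. They say nothing on how often biopsy effects precede dosing, or on how long the nausea, vomiting and confusion seen in the earlier study lasted, so no frequency can be built on either.

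Few events are likely to be affected. The analysis is descriptive with no testing, and all AEs are listed, so a reclassification can be traced, although a listing does not correct a table. The 8.3 points is the effect of one patient at the planned 12, not an estimate of bias. The conclusion assumes that the rules are applied to dates and that the AE page holds no onset time; the CRF is not among the documents. The edits are worth making because they cost almost nothing and feed every AE summary.

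**What to change.** **SAP 9.4.** Define a TEAE as an AE with onset, or an existing AE with an increase in CTCAE grade, on or after the date of first dose. Count Day 1 events unless they are recorded as pre-dose. This date-based default avoids the need for clock times. Keep the TURBT exclusion as written.

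**SAP 5.1.** In all three start-date bullets, make the stop-date condition a stop on or after the date of first dose. The third bullet is worded differently from the other two (it omits the word *first*), so it needs its own edit. State that the SAP 9.4 tie-break prevails over the imputed date. Events whose recorded dates place them wholly before first dose stay outside, as the default in 5.1 already allows.

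**Protocol.** Reconcile footnote 10 of Table 1, 8.1.1.1 and 8.1.1.2 on whether events between consent and first dose go on the AE page or in medical history.

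**Cost.** A few sentences in the SAP and one protocol clarification. No change to sample size, visits or the data the documents already require.

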## **9.5 Clinical Laboratory Evaluation**

Laboratory parameters (clinical chemistry, hematology, urinalysis) will be summarized using descriptive statistics at baseline and at each post-baseline time point. Changes from baseline will also be summarized.

Graded laboratory abnormalities will be defined using the grading scheme based on NCI CTCAE (5.0). The incidence of treatment-emergent laboratory abnormalities, defined as values that increase at least one toxicity grade from baseline at any time post baseline up to and including the date of last dose of study drug, will be summarized by Grade. If baseline data are missing, then any graded abnormality (i.e., at least a Grade 1) will be considered treatment emergent.

All laboratory parameters and pregnancy test results will be provided in listings.

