1.3. Schedule of Assessments

The schedule of assessments is shown in [Table 1](#).

Table 1. Schedule of Assessments

Study Procedure	Screening Period	Treatment Period					Follow-up Period / ET ¹
	Study Days: D -28 to D -1	D1	D2	D3	D4	D5	D35
Study Visits:	V1	V2	V3	V4	V5	V6	V7
Informed consent	X						
Cystoscopy / cold cup biopsy	X						
Inclusion/exclusion criteria	X	X					
ECOG Performance Status	X						
Medical history	X						
Pregnancy test ²	X	X					X
MUGA or ECHO	X						
Chest X-ray or CT scan	X						
Obtain tumor tissue sample ³	X					X	
Hematology ⁴	X	X		X		X	X
Clinical chemistry ⁵	X	X		X		X	X
Urinalysis ⁶	X	X		X			X
Full physical exam ⁷	X						X
Assess for physical symptoms/toxicities ⁷		X	X	X	X	X	
Vital signs ⁸	X	X	X	X	X	X	X
ECG ⁹	X	X				X	X
Adverse events ¹⁰	X	X	X	X	X	X	X
Concomitant medications ¹¹	X	X	X	X	X	X	X
PK blood sample ¹²		X				X	
PK urine sample ¹³		X				X	
Body surface area ¹⁴		X					
CPX-POM infusions ¹⁵		X	X	X	X	X	
TURBT ¹⁶						X	

Abbreviations: AE = adverse event; ALT = alanine aminotransferase; aPTT = activated partial thromboplastin time; AST = aspartate aminotransferase; BSA = body surface area; BUN = blood urea nitrogen; CPX-G = ciclopirox glucuronide; CPX-POM = ciclopirox phosphoryloxymethyl ester; CT = computed tomography; D = day; ECG = electrocardiogram; ECOG = Eastern Cooperative Oncology Group; EDTA = ethylenediamine tetraacetic acid; eGFR = estimated glomerular filtration rate; ELISA = enzyme linked immunosorbent assay; ET = early termination; GGT = gamma glutamyl transferase; IV = intravenous; LC-MS/MS = liquid chromatography-tandem mass spectrometry; MUGA = multi-gated acquisition; PD = pharmacodynamic; PK = pharmacokinetic; PT = prothrombin time; QTc = corrected QT interval; RBC = red blood cell; RC = radical cystectomy; SAE = serious adverse event; TURBT = transurethral resection of a bladder tumor; V = visit; WBC = white blood cell.

1. Safety follow-up assessments will be performed within 30 days (± 3 days) after the last dose of CPX-POM. Or, in the event that a patient discontinues from the study prematurely, the site will make every effort to perform the assessments listed for this study visit.
2. Pregnancy tests will be required only for women of childbearing potential at Screening and before dosing on Day 1. Urine or serum pregnancy tests are acceptable.

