8.1.3.7. Clinical Laboratory Assessments

All protocol-required laboratory assessments, including hematology (including complete blood count), clinical chemistry (including comprehensive metabolic panel), and urinalysis must be conducted in accordance with the Study Procedures Manual and the Schedules of Assessments ([Table 1](#)).

Abnormal laboratory tests that are clinically significant should also be recorded as AEs on the CRF, or as medical history if noted during Screening.

A listing of clinical laboratory tests to be performed is provided in [Table 3](#).

Table 3. Listing of Required Screening and Safety Laboratory Parameters

Laboratory Assessments	Parameters		
Hematology (CBC with differential)	
 • Hemoglobin • Hematocrit • Platelet count • RBC count • Reticulocytes 	WBC Count with Differential	
 • Neutrophils • Lymphocytes • Monocytes • Eosinophils • Basophils
Clinical Chemistry (including CMP)	
 • Potassium • Sodium • Chloride • Glucose • BUN • Creatinine • Creatinine clearance 	
 • ALT • AST • GGT • Alkaline phosphatase • Direct bilirubin • Indirect bilirubin • Total bilirubin 	
 • Total protein • Albumin • Calcium • Bicarbonate • Magnesium • Phosphate • Lipase • Amylase
Routine Urinalysis	
 • Color • Turbidity • pH • Specific gravity • Glucose • Ketones 	
 • Nitrites • Bilirubin • Urobilirubin • Protein • RBCs • WBCs 	
 • Epithelial cells • Casts • Crystals • Bacteria • eGFR (Screening only)
Other	Serum or urine hCG pregnancy test (for women of child bearing potential)		

Abbreviations: ALT = alanine aminotransferase; aPTT = activated partial thromboplastin time; AST = aspartate aminotransferase; BUN = blood urea nitrogen; CBC = complete blood count; CMP = comprehensive metabolic panel; eGFR = estimated glomerular filtration rate; GGT = gamma glutamyltransferase; hCG = human chorionic gonadotropin; MCH = mean corpuscular hemoglobin; MCV = mean corpuscular volume; PT = prothrombin time; RBC = red blood cell; WBC = white blood cell.

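### The only graded incidence computed from laboratory values stops at the date of last dose, so the Day 35/early-termination labs collected for safety follow-up cannot enter it

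*SAP*

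**What the plan says.** SAP 9.5 defines a laboratory abnormality as treatment-emergent when the value rises at least one CTCAE grade from baseline "at any time post baseline up to and including the date of last dose of study drug". Protocol 9.5.2 uses the same cut-off, so the two documents agree. SAP 9.5 plans no other graded laboratory table. The only shift table in the SAP is for overall ECG interpretation (SAP 9.8).

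Laboratory collection does not stop at the last dose. Table 1 schedules all three panels at the follow-up/early-termination visit, and SAP section 3 says patients are followed for at least 30 days after the last dose for safety. If a patient leaves early, footnote 1 says "the site will make every effort to perform the assessments listed for this study visit".

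Late values have two other places to go:

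- **By-visit summaries and listings.** SAP 9.5 summarizes values and changes from baseline at each post-baseline time point and lists every result. SAP section 5 includes the minimum and maximum in continuous summaries.
- **Adverse event tables.** Protocol 8.1.3.7 says "Abnormal laboratory tests that are clinically significant should also be recorded as AEs on the CRF". Protocol 9.5.1 defines a treatment-emergent event as "any AE that begins on or after the date of first dose of CPX-POM", with no end at last dose. SAP 9.4 tabulates "TEAEs by system organ class, preferred term, and highest intensity", but says of its treatment-emergent events "This will not include AEs that are due to the operative TURBT procedure".

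**The concern.** Characterizing safety and dose tolerance is the primary objective, and the graded incidence in SAP 9.5 is the only one that comes from the laboratory values themselves rather than from investigators' event reports. A grade rise first seen at Day 35, or at a termination draw on a date after the last dose, cannot contribute to it. Whether that rise is ever counted as a graded event then depends on someone choosing to record it as an adverse event, and on its not being attributed to surgery. A rise that does not pass this route is visible only as one value in a listing or as part of an ungraded by-visit summary, neither of which gives the number of patients whose grade increased.

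**Working it through.** The plan states no figure on this point, and the sample size of 12 has no calculation behind it (SAP section 4), so there is nothing to reproduce. The check is a count of scheduled draws inside and outside the window.

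**Inputs**

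- Baseline is Visit 2, Day 1 (SAP 9.1).
- Dosing is on Days 1 to 5 (Protocol 6.1.4), so the last dose is on Day 5 for a patient who receives all doses.
- Post-baseline draws in Table 1: hematology on Days 3, 5 and 35; chemistry on Days 3, 5 and 35; urinalysis on Days 3 and 35 (none on Day 5).
- Follow-up is 30 ± 3 days after the last dose (Table 1 footnote 1): 5 + 27 = Day 32 to 5 + 33 = Day 38. Protocol 8.1.1.2 gives 28 ± 5 days instead: 5 + 23 = Day 28 to 5 + 33 = Day 38. Under either, the visit falls well after the window closes.

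**Rule.** A draw can count if its date is after baseline and on or before the last-dose date.

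**Result.** Draws that cannot count, out of post-baseline draws. For early stoppers this assumes no further treatment-period draws and a termination draw on a date after the last dose.

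| Last dose | Hematology | Chemistry | Urinalysis |
|---|---|---|---|
| Day 5 | 1 of 3 | 1 of 3 | 1 of 2 |
| Day 3 or 4 | 1 of 2 | 1 of 2 | 1 of 2 |
| Day 1 or 2 | 1 of 1 | 1 of 1 | 1 of 1 |

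A patient in the last row has no scheduled draw that can enter the incidence. Because the cut-off is a date, a termination draw on the same date as the last dose would count; the gap concerns later dates only. These are counts of draws, not of gradable parameters: much of the urinalysis panel (color and turbidity, for example) is descriptive.

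**Where a late rise can still be counted.** Suppose a grade increase is first seen at Day 35.

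1. SAP 9.5 graded incidence: no, because the date is after the last dose.
2. By-visit summaries and listings: the value appears, but no count of patients with a grade rise results.
3. SAP 9.4 event tables: yes, if it is recorded as an adverse event and is not due to TURBT. The protocol's instruction to turn a laboratory value into an event covers those judged clinically significant. It does not forbid recording others, but it does not require it.

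The documents give no rate for late grade rises, so the number of patients affected cannot be estimated from them.

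**The case against.** The strongest reply is that the cut-off is a deliberate and sensible on-treatment window. The protocol's background section puts the half-life of CPX at 2 to 6 hours with no accumulation. Thirty days is 30 × 24 = 720 hours, which is at least 720 / 6 = 120 half-lives. TURBT takes place 2 to 6 hours after the last dose, so later values may reflect surgery. With about 12 patients in one arm, a reader can go through the listings patient by patient, and the minimum and maximum in the by-visit summaries show extremes.

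Most of this stands. It supports keeping the on-treatment incidence. It does not rule out delayed toxicity, and surgical confounding is a reason to report late rises separately rather than leave them ungraded. Nor does the date cut-off wholly exclude surgical effects: Table 1 does not time the Day 5 draw relative to TURBT, so a Day 5 value inside the window may also be post-operative.

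Three stronger readings are tempting, and the documents do not support them:

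- *The Day 35 data are discarded.* They are summarized and listed; only the graded count omits them.
- *The plan contradicts itself, because treatment-emergent has no end date for events but ends at last dose for laboratory values.* Each definition is explicit, and the laboratory rule is the same in protocol and SAP. These are two conventions.
- *Unrelated late abnormalities can never be recorded as events.* Table 1 footnote 10 does say "Starting at TURBT, only AEs related to CPX-POM treatment should be recorded". But Protocol 8.1.1.1 says events throughout the study, "including the follow-up off study medication period should be recorded as an AE", and Protocol 8.1.1.2 also collects all events through follow-up. That conflict is a separate matter, and those passages must be reconciled. The present point holds whichever governs, because the SAP 9.5 count ends at last dose either way.

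**Conclusion.** The point holds as a coverage gap, and closing it is a cheap improvement. It is not an error in the on-treatment definition. For a completer, one scheduled post-baseline draw per panel falls outside the only value-based graded incidence. For a patient who stops after Day 1 or 2 with later termination labs, every one does. No hypothesis test, power statement or decision rule is affected; what is lost is a graded description of the follow-up period for the primary objective.

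The conclusion rests on Table 1 as scheduled, on the last-dose date being applied literally, and on no graded laboratory output being planned beyond SAP 9.5. Protocol 9.5 speaks generally of summarizing the frequency of abnormalities, but the specific laboratory sections define only the count that ends at last dose. The textual reading is secure; the practical benefit depends on how often late rises occur, which is unknown.

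**What to change.** Change SAP 9.5 only. The opening of Protocol section 9 describes itself as a summary and leaves the finalized analysis plan to the SAP, so a protocol amendment is not needed. Keep the on-treatment incidence as it is and add, for example:

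> For gradable hematology and chemistry parameters, a shift table will present baseline CTCAE grade against the worst grade recorded after the date of last dose through the Follow-up/Early Termination visit. Patients whose grade in this period exceeds their worst on-treatment grade (or their baseline grade, if there is no on-treatment value) will be flagged. The table will be labelled as including the post-TURBT period and not as drug-attributed. Patients with no value in the period will be shown as not assessed.

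A shift table suits this better than a second incidence: a rise that began on treatment and persists is shown as a persisting grade, and the flag isolates what is new or worse after the last dose.

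The cost is one short paragraph and one extra table, with no new visits or samples. The downside is that post-TURBT values may reflect surgery, which the label must make plain.
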